The study is a prospective, randomized, multi-center trial designed to demonstrate the safety and efficacy of the C-Pulse[®] System in relieving heart failure symptoms in patients with ACC/AHA Stage C, NYHA Class III to ambulatory Class IV heart failure. Reduction in heart failure symptoms will be demonstrated by increased freedom from heart failure related hospitalization or death in subjects implanted and treated with the C-Pulse System as compared to a concurrent, randomized control group receiving standard optimal medical therapy (OMT).

Patients will be enrolled into the trial upon providing informed consent. Procedures related directly to the study must not be performed prior to informed consent. Following confirmation of subject eligibility, subjects will be randomized to one of two treatment arms, Treatment or Control, in a 1:1 allocation utilizing a random permuted block design stratified by study center. The Treatment group subjects will receive the C-Pulse[®] System with immediate therapy following implant and OMT while the Control group will continue on OMT. The subjects will not be allowed to cross-over from the assigned group (i.e. a control will not be allowed to receive a C-Pulse). If a treatment subject is explanted, it will be reported in the study analysis per the statistical methods section.

This study will include up to 40 centers in the US and potentially some Canadian centers. The study population will include 388 patients. All subjects who meet eligibility requirements and sign study consent will then be randomized following the baseline testing completion. The follow-up period will be for a minimum of 12 months to assess the safety and efficacy. To facilitate the analysis of the therapeutic effect, it is desired that the system be used all the time. The subject must limit disconnection to a minimal amount of time allowed for personal convenience such as hygiene. The Driver logs subject usage automatically and stores this usage into the system files.

Subjects will be followed for up to five years.

If a subject undergoes anesthesia for the purpose of C-Pulse implantation but does not receive a C-Pulse System, the subject will be followed for 30 days for safety or until they are discharged, whichever occurs first.

[figure not shown]

Figure 1. Study Design Flowchart

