In the event the subject becomes lost to follow-up, the investigational site should make two documented attempts to contact the subject. A Study Exit record must be completed and the subject will no longer be followed in the clinical study.

Data Collection Overview

A review of patient files is required to determine preliminary eligibility according to patient inclusion and exclusion criteria. Baseline data including functional tests must be collected no more than **30** days prior to randomization. Baseline imaging such as echo and CT scans must be collected no more than 90 days prior to randomization. See the data collection table for details.

Follow-up data will be collected at the time of implant, hospital discharge, at planned follow-ups (6 week, 3, 6, 12, 18-month and annually from the implant date thereafter up to 5 years). All serious adverse events will be collected throughout the study until closure.

All study subjects will follow the prescribed follow-up scheduled despite randomization. Day 0 for the treatment group will be the day of implant. Day 0 for the Control Group will be the day of randomization. Each group will continue with optimal medical therapy for the duration of the study, including all standard of care medications and treatments including transplant, VAD, etc. If the subjects are transplanted or placed on another device they will be censored from the primary endpoint analysis and study exited. Subjects implanted with the C-Pulse will be followed until device removal. If the PIL is explanted and not replaced, the subject will be followed for safety until removal of the entire system.

Data will be collected via electronic data capture (EDC) screens referred to as e-case report forms (eCRFs). Echocardiogram tapes and digital storage media must be documented in the patient medical record for source documentation.

Table 1, below outlines the data collection with the appropriate follow-up time windows.

Table 1. Follow-up Windows

Evaluation	Time Window
Pre-Implant Evaluation	No more than 30 days prior to implant
Randomization	Post Baseline Testing and Pre-Implant
Implant	Day 0 (Treatment Group) – Implant Day 0 (Control Group) – Randomization
Pre-Discharge	Within 36 hours prior to discharge
6 – week follow-up	Days 42 ± 7 Post-Implant
3 – month follow-up	Days 90 ± 14 Post-Implant
6 – month follow-up	Days 180 ± 30 Post-Implant
12 – month follow-up	Day 365 ± 30 Post-Implant
18 – month follow-up	Day 540 ± 30 Post-Implant

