Data will be recorded on the eCRFs, imaging and medical record report will be used for source documentation.

CT Scan (Baseline and 12 month follow-up visit only)

A 1-2 mm slice thoracic CT scan is required at Baseline and at 12 month visit only (12 month visit should be ECG Gated) for treatment subjects. Control subjects only require a baseline CT scan.

Data required from the procedure include:

- Sagittal and coronal images shall be reconstructed at mid-systole and mid-diastole to measure narrowest mid ascending aortic luminal dimensions (i.e. with Cuff inflated and deflated).

Assessment will be made of the aortic diameter and presence of any calcific aortic disease. Data will be recorded on the eCRFs, imaging and medical record report will be used for source.

Six Minute Hall Walk Test (Baseline, 3, 6, 12, 18 month and annual follow-up visits)

The subject must perform a six-minute hall walk test (6MHW) at Baseline and one 6MHW test at 3, 6, 12, 18 months and annually thereafter with the C-Pulse. Detailed information is included in the Appendix H.

Two 6MHW tests will be performed at the Baseline visit with at least one hour between the two tests.

During each test, a record will be taken for the time to complete the first 15 feet of the 6MHW as a frailty measure. The time taken for the first 15ft and the distance traveled in 6 minutes will be recorded on the eCRFs and the source records.

Data will be completed on the eCRFs, source documentation will be the worksheet provided by Sunshine Heart Inc. along with the final measurement recorded in the medical record.

Quality of Life Assessment (Baseline, 3, 6, 12, 18 month and annual follow-up visits)

The subject must complete the Minnesota Living with Heart Failure Questionnaire (MLWHF) and the Kansas City Questionnaire (KCCQ) at Baseline, 3, 6, 12, 18 month and annual visits thereafter.

Data will be completed on the Baseline and Follow-up eCRFs. The eCRFs will be used as source documentation for the QoL questionnaires.

NYHA Class Assessment (Baseline, 3, 6, 12, 18 month and annual follow-up visits)

A clinician at each site shall complete the NYHA Classification at Baseline, 3, 6, 12, 18 month and annual visits thereafter.

Data will be completed on the eCRFs. The eCRFs will be used for source documentation.

Concomitant Cardiac Medications (Baseline, implant, pre-discharge, 6 week, 3, 6, 12, 18 month and annual follow-up visits)

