The patient should not be discharged if any of the following issues are present:

- Unresolved system malfunction
- Back-up equipment is not available
- Unresolved adverse event that threatens patient safety
- Patient requires any treatment for disease, illness, mental or physical disability that cannot be provided outside the hospital

Post-Implant Follow-up Testing and Data Collection

Post-Implant Testing and Data Collection Summary

The complete reference list of post-implant testing and data collection that will be performed at each time point is included in Table 3.

Unscheduled Follow-up Visits

If subjects are seen between protocol-scheduled visits because of clinical symptoms requiring readmission, device reprogramming, etc. a follow-up form must be completed with all appropriate sections. In addition, all serious adverse events must be documented throughout the study.

System Modifications

Immediately contact Sunshine Heart clinical support team if a need is suspected for system modification (internal component or system replacement). In the event that the C-Pulse[®] System requires modification (e.g. Cuff or PIL) data collection must be recorded on the eCRFs along with an adverse event form. Modifications should be done only in communication with Sunshine Heart Inc. clinical personnel, unless the modification is a medical emergency, in which case, Sunshine Heart Inc. clinical personnel should be notified as soon as possible. In addition, the eCRF data collection must be completed documenting the removal of the existing device or component. The explanted C-Pulse[®] component(s) should be processed according to the Explant Handling Instructions and returned to Sunshine Heart Inc. or designee.

In the event of a system modification, including component removal, reposition or replacement of the entire C-Pulse[®] System, the follow-up schedule for the subject will remain unchanged (i.e. the subject should continue to be seen for follow-up and associated forms should be completed based on the original follow-up schedule). All serious adverse events should be reported and classified by the investigator. Additionally the CEC will provide further classification of adverse events.

Adverse Event Reporting

Overview

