Report all associated adverse events. Update the device tracking records with all products. If the device is not returned to Sunshine Heart Inc., justification must be provided in the log.

Subject Withdrawal and Study Exit

A Study Exit record shall be completed if subject is unable to or refuses to continue participation in the study. Notify the Sunshine Heart clinical support team as soon as possible upon learning of a subject withdrawal/study exit.

If the subject fails to comply with follow-up visits, the study center must make repeated attempts to contact the subject. Each attempt to contact the subject must be documented in the subject's records and in the database.

If the subject officially withdraws from the study, the investigator will document the reason for withdrawal and indicate any relationship of the withdrawal to the study or the device on the eCRF.

If a subject withdraws from the study at any time, there will be no penalty or loss of future medical care.

STATISTICAL METHODS AND DATA ANALYSIS

Analysis Population

All randomized subjects will be included in the evaluation of the primary efficacy objective. Subjects will not be allowed to cross-over. All subjects implanted with the C-Pulse System will be included in the evaluation of the primary safety objective. In the event a randomized subject does not receive the implant or does not receive the randomized therapy, the subject will be analyzed according to the randomized assignment for the primary analyses. Additional supporting analyses of the primary efficacy endpoint will be conducted (as treated and per-protocol) which exclude subjects who do not receive the randomized treatment or those with major protocol deviations. The defined analysis cohorts are:

- Intent to treat: All randomized subject irrespective of treatment actually received (primary efficacy analysis)
- As treated: All randomized subjects receiving treatment as randomized
- Per protocol: All randomized subjects without major protocol deviations

Primary Efficacy Endpoint

The primary efficacy endpoint is defined as freedom from worsening heart failure related hospitalization, LVAD implant, heart transplant, and death.

The primary efficacy endpoint includes all occurrences of worsening heart failure events and will be analyzed utilizing a multiple failure time analysis.

Hypotheses

H_0 : HR=1,

H_A : HR \neq 1,

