The poolability of the primary efficacy endpoint across clinical sites will be assessed using a covariate adjusted proportional hazards regression model including an interaction term for clinical site and treatment group. In the event statistical evidence of a difference in treatment effect by site is found, an analysis utilizing a random effects model with a random effect for site will be conducted.

Type I Error Control for Secondary Objectives

The secondary efficacy objectives will be tested in a hierarchical fashion in the order listed only in the event the primary efficacy objective is met, thereby preserving an overall Type I error rate of 5%.

Handling of Missing Data

For the primary efficacy analysis, subjects lost to follow-up or explanted will be censored at the date of the last assessment.

Additional analyses of the follow-up assessments of KCCQ, six minute walk and LVEF will be conducted to assess the impact of missing data at month 12. The Wilcoxon Sign-Rank test with the worst rank imputed for data missing due to death, LVAD transplant, heart transplant or explant (in order of time to outcome) will be used to assess treatment differences in the continuous parameters while including subjects who withdrew from randomized treatment prior to the 12 month assessment. Multiple imputation analyses will be conducted to assess the robustness of the study results against data missing due to losses to follow-up and study non-compliance or un-interpretable test results.

Impact of Covariates on the Potential Treatment Differences

Additional exploratory statistical analyses of the primary and secondary study results will be conducted to assess for impact of selected baseline and follow-up parameters on the observed treatment differences. This will involve the stratification of results by categorical parameters and covariate adjusted regression analyses for the assessment of interaction with randomization assignment. Of particular interest will be an assessment for any treatment differences in the efficacy or safety parameters by gender. Other baseline covariates of interest will include classification based on race/ethnicity, age at implant, INTERMACS profile, NYHA, etiology (ischemic/non-ischemic), CRT/ICD therapy, angina, arrhythmia, hyperlipidemia and diabetes and the continuous covariates of baseline six-minute walk, KCCQ and MLWHF.

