Due to the possible interaction of site infection leading to “Deep” infection or tissue swelling around the intrathoracic gas line and /or ascending aorta an infection procedure monitoring process is recommended. The following process is recommended to reduce risk of injury to the patient.

Infection Monitoring Process:

In the presence of clinical signs (pain, redness, discharge, loss of driveline fixation) and /or microbiological evidence (positive wound culture) of infection (intermittent or chronic) over a 3 month period despite treatment.

Decision Process:

Are there clinical signs or microbiological evidence of infection over a 3 month period despite treatment?

- No: Continue therapy
- Yes: Perform CT or PET scan
 - If scan is positive (i.e. shows evidence of DEEP infection or soft tissue swelling around the intrathoracic gas line and/or ascending aorta or presence of intrathoracic gas), then REMOVE PIL AND CUFF.
 - If scan is negative (i.e. shows no evidence of DEEP infection), REMOVE PIL only.
 - If at the time of surgery there is clinical evidence of DEEP infection (i.e. pus or fluid around the ‘Y’- connector, positive gram stain, and infected tissue) then REMOVE the CUFF also.
- If at the time of CT/PET scan or surgery there is no evidence of DEEP infection, then REPEAT SCAN at 3 months post-op and monitor for clinical signs of infection, if none found then REPEAT SCAN annually.
- NOTE: if wound culture is positive for MRSA, MSSA or Pseudomonas, monitor more frequently with FOLLOW-UP CT-SCAN at 3 months.

Aortic Tissue Sampling Guideline

In the event of a heart transplant, LVAD placement or patient death in the control group, it is requested that a single tissue sample of the ascending aorta should be collected for analysis.

In the event of a heart transplant, LVAD placement or patient death in the treatment group, it is recommended that the C-Pulse system be removed. To ensure evaluation of the system and patient interaction the following process provides guidance on removal of the C-Pulse implanted components at the time of explant, the observations to be recorded and for device return for analysis.

- If possible, return the devices intact and connected. In the event of device dissection, attempt to maintain the connections intact.
- For the Cuff, balloon integrity should be maintained unless histopathological analysis requires dissection.

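### The primary-endpoint censoring rule leaves open whether heart failure events after removal of the percutaneous lead (PIL) alone are counted, and only the device arm is affected

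*Combined protocol and SAP*

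**What the plan says.** Analysis Population sets the primary efficacy cohort as "All randomized subject irrespective of treatment actually received (primary efficacy analysis". Handling of Missing Data then states that, for that same analysis, "subjects lost to follow-up or explanted will be censored at the date of the last assessment". Design points to the statistical section for these cases: "If a treatment subject is explanted, it will be reported in the study analysis per the statistical methods section". The reviewed text does not define *explanted*.

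Data Collection Overview (under Procedures) follows implanted subjects until the device is removed and adds: "If the PIL is explanted and not replaced, the subject will be followed for safety until removal of the entire system". The same section says "All serious adverse events will be collected throughout the study until closure", and Adverse Event Definitions makes in-patient hospitalization a criterion for a serious event. System Modifications treats removal of a component as a modification, after which "the subject should continue to be seen for follow-up and associated forms should be completed based on the original follow-up schedule".

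PIL removal with the Cuff left in place is a planned state. For infection lasting three months despite treatment, Appendix K directs a scan, and then: "If scan is negative (i.e. shows no evidence of DEEP infection), REMOVE PIL only".

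Primary Efficacy Endpoint refers the details of the analysis to a Statistical Analysis Plan. No separate text of that plan is in the reviewed document.

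**The concern.** The PIL joins the Cuff to the Driver, so taking it out without replacement stops therapy. The risk section on device failure says that heart failure symptoms may return when the device stops. Control subjects have nothing to explant. If PIL-only removal counts as explant, and censoring falls at or before removal, then off-therapy events that the sites still report are left out of one arm only. The hazard ratio would then compare device subjects while on therapy with all control subjects, which is not the as-randomized comparison that Analysis Population promises. If subjects who lose the PIL are also at higher risk, censoring them favors the device even when it has no effect. The interim efficacy and futility assessment uses the same endpoint.

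The wording about follow-up for safety adds a smaller uncertainty. It does not say whether efficacy assessments continue, whereas System Modifications keeps the original schedule and forms.

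**Working it through.** **The readings side by side**

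| Meaning of *explanted* | Meaning of *last assessment* | Events after PIL-only removal |
|---|---|---|
| Includes PIL-only removal | Last assessment up to the removal | Dropped |
| Includes PIL-only removal | Last assessment in continued follow-up | Kept up to that assessment |
| Whole system only | Not triggered by PIL removal | Kept until the whole system is removed |

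The text fits all three.

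**Inputs from Primary Efficacy Endpoint Sample Size:** two-sided alpha 0.05, power 0.80, control 6-month freedom from event 0.72, hazard ratio (HR) 0.70, accrual 2.5 years, minimum follow-up 12 months, attrition 10% per year, 265 events, 388 subjects (194 per arm).

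**The plan's own figure first.** Schoenfeld's formula gives 4 × (1.960 + 0.842)² / (ln 0.70)² = 247 events. With exponential hazards and 10% yearly loss, the mean event probability is 0.627, so 247 / 0.627 = 394 subjects, within 2% of 388. The stated 265 is not the number required for 80% power; it matches what 388 subjects yield with no attrition (265.8). It is used below only as the plan's stated count.

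**Illustration of the first reading against counting all events**

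- Control hazard: −ln(0.72) / 0.5 = 0.657 per year. Device hazard on therapy: 0.70 × 0.657 = 0.460 per year.
- Assumed: a share s of the 194 device subjects loses the PIL, on average at month 6 of 12. The off-therapy share of person-time is f = s/2.
- Assumed: the off-therapy hazard is k times control.
- Events left out: 194 × f × 0.657 × k. On-therapy events: 194 × (1 − f) × 0.460.
- HR with all events counted: 0.70 × (1 − f) + k × f.
- Approximate power: Φ(|ln HR| × √265 / 2 − 1.96). At HR 0.70 this is 0.83.

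| s | f | k | Events left out | On-therapy events | HR, all events | Power |
|---|---|---|---|---|---|---|
| 2% | 0.01 | 1 | 1.3 | 88.3 | 0.703 | 0.82 |
| 20% | 0.10 | 1 | 12.7 | 80.3 | 0.730 | 0.73 |
| 2% | 0.01 | 1.5 | 1.9 | 88.3 | 0.708 | 0.80 |
| 20% | 0.10 | 1.5 | 19.1 | 80.3 | 0.780 | 0.52 |

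**Recurrent events over the full follow-up (simulation).** PIL-only removal was assumed at 5, 10 and 20% per year, about 9, 18 and 32% of the device arm. With k = 1, counting all events gives rate ratios of 0.72, 0.73 and 0.76, against about 0.70 with censoring at removal. With k = 1.5 they are 0.75, 0.79 and 0.86.

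**No true effect.** If removal is more likely in sicker subjects (gamma frailty, variance 1, k = 1), censoring at removal gives ratios of about 0.95, 0.90 and 0.84 where the truth is 1.00. If removal is unrelated to risk and k = 1, there is no bias.

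**The case against.** The strongest reply is that the benign readings fit the text better. The censoring rule speaks of subjects explanted, whereas Data Collection Overview speaks of the PIL and, in the same sentence, separates it from removal of the entire system. Appendix K and the feasibility summary in Appendix B mostly use explant for the whole device, and Handling of Missing Data lists it beside death, LVAD and transplant. The censoring date is the last assessment, not the explant date, and a PIL-only subject goes on being assessed. The Statistical Analysis Plan may define the term. All of this stands, and it makes the point an unsettled rule rather than a demonstrated loss of events.

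A reader might infer that sites will stop efficacy testing after PIL removal. The documents do not support that. System Modifications expressly covers component removal and keeps the schedule and forms, and omitted required testing is a protocol deviation. The walk-test wording, "one 6MHW test at 3, 6, 12, 18 months and annually thereafter with the C-Pulse", cannot be a condition of testing, because controls walk too. Worst-rank and multiple-imputation analyses are also planned; they are framed for month 12, so the 18-month walk is the only gap.

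The sizing is also open to challenge. It sets a 12-month first-event rate beside an event count from longer follow-up, and the 20% end has no source. The enrollment halt at more than 8 of 20 exit-site infections (40%) is an infection threshold, not a removal rate; against it, 2% and 20% would mean removal in 1 in 20 and 1 in 2 of those infected. The PIL is replaceable and feasibility infections were managed in outpatients, so the low end is more likely. If some PILs are removed because the heart has recovered, the bias could shrink or reverse.

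**Conclusion.** The point holds as an ambiguity in a stated censoring rule. The rule acts on one arm only, sits inside an analysis declared intent to treat, and has one open reading that discards events already collected. A reader might infer that the plan does censor at PIL removal, or that the primary result would be materially biased. The text establishes neither: other readings keep the events, and no PIL-only removal rate is given.

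Under the unfavorable reading, with constant rates, removal on average at month 6 and an off-therapy hazard equal to control, the effect is negligible at 2% removal (HR 0.70 to 0.703, about 1 point of power). At 20% it is modest (0.730, about 10 points). It is larger if subjects off therapy do worse than control. Removal rate, timing and off-therapy hazard are all assumptions.

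It is worth settling before results by arm are seen, because the choice between readings changes the primary estimate and treating teams know the assignment.

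**What to change.** 1. **Handling of Missing Data.** State that removal of the PIL alone does not trigger censoring; that adjudicated primary events count to the end of the subject's actual follow-up under the intent-to-treat analysis; and that censoring at loss of therapy is a sensitivity analysis only.
2. **Data Collection Overview.** Replace the wording on follow-up for safety with follow-up on the original schedule for all safety and efficacy assessments, with a cross-reference to System Modifications.
3. **Whole-system explants.** Their follow-up ends at device removal, so they remain censored. Acknowledge this as a departure from intent to treat; items 1 and 2 do not remove it.

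The cost is a few sentences. The visits are already scheduled and the events already collected. The downsides are slightly more follow-up work for subjects off therapy and a possibly less favorable device-arm estimate.

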Procedure Related

An adverse event will be considered procedure related if it is a direct result of the implant, explant or modification procedure, which cannot be directly attributed to any particular device or implant tool.

Patient Management Related

An adverse event will be considered related to patient management if it is a direct result of the medical complexities and decision making involved in managing co-morbidities.

Concomitant Medication Related

An adverse event will be considered related to concomitant medication when it is reasonable to believe that the event is directly associated with medications used in conjunction with the investigational device and it is not otherwise specific to the device, procedure or patient management.

Therapy Related

An adverse event will be considered therapy related if it is a direct result of, or is affected by the therapy delivered by the device not just the presence (intended or otherwise) of the investigational device.

Unavoidable Events

The events listed in Table 3 are considered minor and if the onset occurs within the timeframe specified, are not subject to adverse event reporting.

Table 3. Unavoidable Events

Event Description	Timeframe (post-implant)
Anesthesia related nausea/vomiting	24 hours
Low-grade fever (<102 degrees F)	48 hours
Minor incision/exit site pain	72 hours
Minor, localized tenderness, swelling, oozing, etc. at incision sites	72 hours
Early post-operative pain associated with endotracheal tube placement and mechanical ventilation	72 hours
Electrolyte imbalance without clinical sequelae	72 hours
Systolic and diastolic blood pressure changes that do not require treatment or intervention	On-going
Chest tube drainage or blood loss not requiring intervention and hematocrit remaining above 25%	72 hours
Sinus bradycardia and tachycardia that does not require intervention	On-going

Adverse Event Reporting to IRB and Regulatory Agencies for Unanticipated Device Events

The investigator must report any unanticipated adverse device effects (UADE) to the Sponsor (Sunshine Heart) and IRB within 10 days after the investigator first learns of the event. The Sponsor must report any UADE to the regulatory agencies, IRBs and all investigators within 10 days of receipt of notice of the event.

An **unanticipated adverse device effect** is defined as:

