The primary safety endpoint is 12 month freedom from serious adverse events that are adjudicated definitely related to device, therapy or procedure and resulting in either surgical intervention or death. All serious adverse events that are adjudicated by CEC to be definitely related to device, therapy or procedure and result in either surgical intervention or death will be included in the analysis. Events will be reported by number of event and proportion of subjects with event along with the ninety-five percent binomial exact confidence limits. Only first event counts towards the endpoint for each subject.

The proportion of C-Pulse[®] subjects free from serious adverse events that are adjudicated definitely related to device, therapy or procedure and result in surgical intervention or death through 12 months following implant and will be compared to the performance goal (PG) of 0.60.

The hypotheses are:

$$H_0: \Pi \leq PG,$$

$$H_A: \Pi > PG,$$

where Π is the 12 month freedom from serious adverse events that are definitely related to device, therapy or procedure and resulting in either surgical intervention or death and PG is the performance goal. If the lower, two-sided, 95% confidence bound is greater than 0.6 the objective will be met.

Primary Safety Endpoint Sample Size

Sample size was estimated for a combined freedom from serious adverse events adjudicated definitely related to device, therapy or procedure resulting in surgical intervention (to repair, replace or remove the implanted device) or death. The minimum required sample size and total number of device related deaths and device related surgical intervention events was calculated under the following assumptions:

- Significance level = 0.05
- Power = 0.80
- 12 month freedom from serious adverse events definitely related to device, therapy or procedure resulting in either surgical intervention (to repair, replace or remove implanted device) or death event of 70%.
- Minimum follow-up of 12 months

Under the above assumptions a minimum of 182 subjects are required.

Justification for Primary Safety Endpoint Sample Size

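### The primary safety set is tied to receiving the device, so subjects anesthetized for an implant that is not completed most likely fall outside a test that counts procedure-related deaths and surgery

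*Combined protocol and SAP*

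**What the plan says.** Four parts of the combined protocol and SAP bear on this.

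- **Safety set.** Statistical Methods and Data Analysis, Analysis Population: "All subjects implanted with the C-Pulse System will be included in the evaluation of the primary safety objective". The next sentence deals with a randomized subject who does not receive the implant: "the subject will be analyzed according to the randomized assignment for the primary analyses". The cohort list below it attaches intent to treat to the primary efficacy analysis and defines no safety cohort.
- **Endpoint.** Primary Safety Endpoint: 12-month freedom from "serious adverse events that are adjudicated definitely related to device, therapy or procedure and resulting in either surgical intervention or death". The proportion is taken over the 12 months after implant. The objective is met if the lower limit of the two-sided 95% interval exceeds 0.60, with exact binomial limits.
- **Procedure-related events.** Adverse Event Classification calls an event "procedure related if it is a direct result of the implant, explant or modification procedure". The implant operation is therefore within the endpoint's scope.
- **Attempted but not implanted.** Study Description, Design: "If a subject undergoes anesthesia for the purpose of C-Pulse implantation but does not receive a C-Pulse System", then "the subject will be followed for 30 days for safety or until they are discharged, whichever occurs first".

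**The concern.** The endpoint targets harm from the operation as well as from the device. Summary of Implant Procedure has the aorta isolated and measured before the Cuff is secured, and the Risk Analysis lists bleeding, aortic disruption and death among the risks of the procedure. A subject could therefore have a qualifying event before becoming an implanted subject. If such subjects are left out, membership of the safety set is decided by the outcome being studied.

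The timing rules add to the problem. A subject with no implant has no day 0 on the treatment arm's definition. If follow-up stops at 30 days or discharge, whichever comes first, a 12-month outcome cannot be determined for that subject. The test is pass or fail, and the Secondary Efficacy Endpoints section makes hypothesis testing of the secondary endpoints depend on it, so the denominator should not be open to choice once data are in.

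**Working it through.** **Inputs.** From Primary Safety Endpoint and its sample-size section: goal 0.60, assumed freedom 0.70, significance level 0.05 (two-sided limits), power 0.80, exact binomial limits. From Study Size and Duration: 194 treatment subjects. The number of aborted implants (k) and their event rate (q) are not in the documents. They are assumptions here, shown over a range.

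**Step 1: the plan's own figure.** One-sample normal approximation:

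n = [1.960 × √(0.60 × 0.40) + 0.842 × √(0.70 × 0.30)]² / 0.10² = 181.13, rounded up to 182.

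The stated minimum of 182 reproduces. The sample size is not in question.

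**Step 2: pass limits.** The exact lower limit for x event-free of n is the 2.5% quantile of Beta(x, n − x + 1). The smallest passing counts are 123 of 182 and 131 of 194.

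**Step 3: effect of excluded events at the pass limit.** Each added subject is an aborted implant with a qualifying event.

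| Event-free / n | Lower limit | Goal met? |
|---|---|---|
| 123/182 | 0.6026 | yes |
| 123/183 (one added) | 0.5990 | no |
| 131/194 | 0.6045 | yes |
| 131/195 (one added) | 0.6011 | yes |
| 131/196 (two added) | 0.5977 | no |

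With the number of attempts fixed at 194, 128/190 implanted passes (0.602). Counting four aborted subjects with events gives 128/194, which fails (0.588).

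**Step 4: direction of the bias.** Let overall freedom be 0.60 across 194 attempts. Freedom among the implanted is then

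p = [0.60 × 194 − k(1 − q)] / (194 − k).

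This exceeds 0.60 only if q is above 0.40. For k = 4 and q = 1, p = 116.4/190 = 0.613. For k = 4 and q = 0.30, p = (116.4 − 2.8)/190 = 0.598.

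**Step 5: false-pass probability.** This is the binomial probability that the implanted-only result reaches its pass limit (129 of 192, 128 of 190, 127 of 188, 124 of 184), given p from step 4.

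| Aborted (k) | q = 30% | q = 40% | q = 50% | q = 100% |
|---|---|---|---|---|
| 2 | 2.2% | 2.4% | 2.6% | 3.6% |
| 4 | 1.9% | 2.2% | 2.5% | 4.8% |
| 6 | 1.6% | 2.0% | 2.4% | 6.4% |
| 10 | 1.6% | 2.3% | 3.3% | 13.8% |

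The reference is the nominal one-sided 2.5%. With no aborted implants the attained level at n = 194 is 1.8%. That is a low point caused by discreteness (the level is 2.4% at n = 192 and 2.2% at n = 190), so 1.8% is a poor baseline for judging the increase.

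**The case against.** The strongest reply is that exclusion is not established. Analysis Population says that implanted subjects are included. It does not say that nobody else is, and the next sentence assigns non-implanted subjects to their randomized arm for the primary analyses, in the plural. This stands as far as it goes: a reader might infer that the plan admits implanted subjects only, and the text does not quite say so. Exclusion is still the likelier reading, because intent to treat is tied to efficacy, the clock runs from implant, and follow-up of these subjects can end at discharge.

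The second reply is about direction. An operation closed without harm removes an event-free subject, which works against the device. This also stands. A reader might infer that the error rate is above nominal in general, but the table in the working does not support that. At event rates of 40% or less among aborted cases, the false-pass probability stays below 2.5%. The 13.8% figure needs ten aborted implants, all with definitely related events, and nothing in the documents suggests that.

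Three narrower replies have some force:

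- The safety sample-size section limits surgical intervention to repairing, replacing or removing the implanted device. If that governs, only death could count for a subject with no device. The endpoint definition carries no such limit.
- A reader might infer that the fit check at surgery is the final suitability decision. The protocol does not call it that. CT screening and the aortic diameter limits come earlier, and the Design section gives no reason for non-receipt.
- Deaths must be documented, the Clinical Events Committee adjudicates adverse events and deaths, and adverse events and mortality are summarized by group. That makes events visible up to study exit, but does not bring them into the primary safety test.

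The protocol also refers details of the efficacy analyses to a Statistical Analysis Plan. The safety section makes no such reference, and no fuller definition of the safety set appears in the text available.

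**Conclusion.** The point holds as a gap in the definition of the safety set that should be fixed, with moderate confidence. Followed as most naturally read, the plan drops attempted-but-not-implanted subjects from an endpoint that counts procedural harm. Read the other way, it includes subjects who have no day 0 and no 12-month follow-up. Either way, the safety set, the clock and the follow-up rule do not fit together.

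The size is conditional. One or two excluded events reverse a result at the pass limit. The false-pass probability rises clearly only if most aborted cases have qualifying events. The calculations assume independent subjects, complete 12-month outcomes and true freedom of exactly 0.60 over 194 attempts, and both the aborted-implant rate and its event rate are assumed. The documents do not support a claim that the test is biased toward the device whatever those rates are.

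**What to change.** - In Analysis Population and Primary Safety Endpoint, define the primary safety set as all treatment-arm subjects in whom anesthesia for implantation was started, with day 0 the day of that procedure. Restrict the as-randomized sentence to efficacy, or reword it to agree.
- Reconcile the follow-up cut-off in Design with the 12-month endpoint by collecting endpoint events (at least vital status and related surgery) to 12 months for these subjects. The intent-to-treat efficacy analysis also needs their outcomes beyond discharge.
- State whether surgical intervention covers any related surgery or only surgery to repair, replace or remove the implanted device, so that the endpoint and the sample-size text agree.
- Report the implanted-only result as supportive.

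The cost is a few wording changes and data collection on what should be a small number of subjects. The required 182 does not change. The safety estimate may come out slightly less favourable.
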